11.4.4 Effective Methods of Contraception for Allakos Studies

This section applies to study subjects who are women of childbearing potential (WOCBP) and male study subjects whose sexual partners are WOCBP.

Abstinence is the only birth control method that is 100% effective in preventing pregnancy. For subjects who do not practice abstinence, Allakos recommends that study subjects use highly effective methods of contraception, which include:

- **Permanent Sterilization:** Tubal ligation, vasectomy – 99% effective
- **Long-Acting Reversible Contraceptives (LARC):**
 - IUD – 99% effective
 - Implantable rod (matchstick sized rod that contains progestin hormone implanted under the skin of the upper arm; prevents ovulation) – 99% effective
- **Contraceptive Injection:**
 - Intramuscular or subcutaneous injection of progestin hormone every 3 months – 96% effective
- **Short-Acting Hormonal Methods:**
 - Oral contraceptives or patch – 91% effective
 - Vaginal contraceptive ring (releases 2 hormones, progestin and estrogen, to prevent ovulation) – 91% effective

Note: Effectiveness rates obtained from the Birth Control Guide on the FDA web site ([FDA, 2021](#)).

Barrier and other methods not listed above when used together as dual methods such as a condom + diaphragm or condom + spermicide are less effective methods, therefore these dual methods are not recommended as they could increase the risk of becoming pregnant during the study or follow-up period. When using dual methods, at least 1 of the methods should be a highly effective method of contraception.

Subjects, who entered the study using dual methods of contraception that do not include at least 1 of the highly effective methods of contraception, are allowed to continue in the study but must be informed of the risks of not using highly effective methods of contraception.

11.4.5 Urinalysis

Urine samples will be processed and shipped in accordance with the central laboratory manual and laboratory kit instructions. Urine will be obtained on Extension Days 1, 197, and 512 or 35 (± 3) days after last dose of study drug if ET. If already collected within the last 28 days as part of the last study visit for AK002-016, a duplicate collection is not required on Extension Day 1. A central laboratory will analyze the urine sample for specific gravity, pH, protein, glucose, ketones, blood, and leukocyte esterase.

11.4.6 Anti-AK002 Antibodies

Serum samples for ADA determination will be processed and shipped frozen in accordance with the central laboratory manual and laboratory kit instructions. Blood will be collected for determination of ADA predose on Extension Days 1, 197, and 512 (± 3 days) or 35 (± 3) days after last dose of study drug if ET. If already collected within the last 28 days as part of the last study visit in AK002-016, a duplicate collection is not required on Extension Day 1. For patients entering from Study AK002-012, a baseline collection is required prior to the first dose of study drug in AK002-016X.

A central laboratory will analyze the sample for ADA using a validated assay method. Specific information on ADA sample collection, processing, storage, and shipment will be provided in the central laboratory manual. Blood samples for ADA will also be collected anytime an immunogenicity-related AE occurs.

11.4.7 Pharmacokinetics and Storage

Blood samples for serum PK assessments will be processed and shipped frozen in accordance with the central laboratory manual and laboratory kit instructions. Blood will be collected for PK assessments predose on Extension Days 1, 197, and 512 (± 3 days) or 35 (± 3) days after last dose of study drug if ET. If already collected within the last 28 days as part of the last study visit in AK002-016, a duplicate predose collection is not required on Extension Day 1. For patients entering from Study AK002-012, a baseline collection is required prior to the first dose of study drug in AK002-016X.

AK002 concentrations will be determined by the central laboratory or designee using a validated ELISA method. Specific information on PK sample collection, processing, storage, and shipment will be provided in the central laboratory manual.

11.4.8 Histamine and Tryptase

If anaphylaxis is suspected, a blood sample should be obtained for plasma histamine and tryptase levels within 1–2 hours of the onset of symptoms. The sample should be sent to the central laboratory for processing.

11.4.9 IgE

Blood will be collected for determination of serum IgE levels and sent to the central laboratory for processing. Blood will be collected predose on Extension Day 1 and Day 512 (± 3) or 35 (± 3) days after last dose of study drug if ET. If already collected within the last 28 days as part of the last study visit in AK002-016, a duplicate predose collection is not required on Extension Day 1. For patients entering from Study AK002-012, a baseline collection is required prior to the first dose of study drug in AK002-016X.

11.4.10 COVID-19 Testing

Testing for COVID-19 is not required for this study but may be implemented by the study site at any time during the study due to safety regulations or procedures. Testing for COVID-19 may be individually mandated by EGD facilities and, if this is required, will be consented through the site and not listed in the AK002-016X informed consent form (ICF).

12. Evaluations and Procedures by Visit

Written, informed consent will be obtained before any study procedure is performed.

General Information:

- Evaluations and procedures by visit are shown in [Table 1](#).
- All recorded clock times should utilize a 24-hour clock.
- Extension Day 1 is the day of the first infusion in this extension study.

12.1 Prior to Extension Day 1

The following procedures will be performed prior to Extension Day 1:

- Obtain written informed consent ***prior*** to patient receiving premedication.
- Verify eligibility for the study.
- Patient to self-administer 80 mg oral prednisone (or approved alternative) 12–24 hours prior to predicted infusion start.

12.2 Extension Day 1 – First Day of Dosing

The following procedures will be performed prior to study drug infusion:

- Confirm continuing eligibility for the study.
- Activate patient access to ViedocME website and instruct patient on use of the website to complete the questionnaire(s). Use the ePRO Teaching Tool (Appendix 4) to remind patients on the use of the electronic platform.
- Have patient complete SF-36 Health Survey. Obtain from last study visit of AK002-016 if the visit occurred within 28 days prior to Extension Day 1.
- Determine body weight (in kg).
- Enter PID and body weight (in kg) into IRT.
- Document any changes in baseline diet. Obtain from last study visit of AK002-016 if the visit occurred within 28 days prior to Extension Day 1.

- Collect vital signs within 30 minutes of the start of the infusion.
- Perform symptom-directed physical examination, as needed. Obtain from last study visit of AK002-016 if the visit occurred within 28 days prior to Extension Day 1.
- Collect blood samples for CBC, blood chemistry, IgE, ADA, and PK. Obtain from last study visit of AK002-016 if the visit occurred within 28 days prior to Extension Day 1. Differential cell counts from AK002-016 will remain blinded.
- Collect urine for urinalysis. Obtain from last study visit of AK002-016 if the visit occurred within 28 days prior to Extension Day 1.
- Perform urine pregnancy test. Obtain from last study visit of AK002-016 if the visit occurred within 28 days prior to Extension Day 1.
- The study pharmacist will prepare study drug at **3 mg/kg** using the body weight obtained at the visit or the day prior to Extension Day 1. The final combined volume of the IV bag of study drug + 0.9% NaCl will be **120 mL**.

Note: **100 mL** of the calculated volume of study drug/NaCl mixture will be administered to the patient. The extra 20 mL is to be used to prime the IV infusion line during the preparation of the IV line or to be left over in the infusion bag/tubing when the infusion is completed.

Procedures associated with the infusion of study drug include:

- Infuse 100 mL of study drug over at least 4 hours using an infusion pump. Refer to the Pharmacy Manual for infusion rates. Record the start and stop times of the infusion including any times the infusion is interrupted.
- Collect vital signs within 30 minutes after the start of infusion.
- An unscheduled ADA blood sample may be obtained if an immunogenicity-related AE is suspected. If anaphylaxis is suspected, collect a sample of blood for plasma histamine and tryptase levels within 1–2 hours of the onset of symptoms.

The following procedures will be performed after study drug infusion:

- Collect vital signs within 30 minutes after the end of infusion.
- Collect CBC with differential 1 hour (± 15 minutes) after the end of infusion.
- Observe the patient for at least 1 hour after the end of infusion.

Concomitant medication use and AE (including AESI and SAE) will be documented throughout the clinic visit.

12.3 Extension Day 29 (± 3) – Dose 2

The following procedures will be performed prior to study drug infusion:

- Have patient complete the SF-36 Health Survey.
- Determine body weight (in kg).
- Enter PID and weight (in kg) into IRT.
- Document any changes in baseline diet.
- Collect vital signs within 30 minutes prior to the start of infusion.
- Collect urine only if patient is of childbearing potential. Conduct a urine pregnancy test.
- Perform symptom-directed physical examination, as needed.
- Collect blood samples for CBC and chemistry.
- The study pharmacist will prepare study drug at **3 mg/kg** using the body weight obtained at the visit. The final combined volume of the IV bag of study drug + 0.9% NaCl will be **120 mL**.

Note: **100 mL** of the calculated volume of study drug/NaCl mixture will be administered to the patient. The extra 20 mL is to be used to prime the IV infusion line during the preparation of the IV line or to be left over in the infusion bag/tubing when the infusion is completed.

Procedures associated with the infusion of study drug include:

- Premedication only to be administered with the written approval of the Medical Monitor.
- Infuse 100 mL of study drug using an infusion pump over at least 2 hours on Extension Day 29. Refer to the Pharmacy Manual for infusion rates. Record the start and stop times of the infusion including any times the infusion is interrupted.
- Collect vital signs within 30 minutes after the start of infusion.
- An unscheduled ADA blood sample may be obtained if an immunogenicity-related AE is suspected. If anaphylaxis is suspected, collect a sample of blood for plasma histamine and tryptase levels within 1–2 hours of the onset of symptoms.

The following procedures will be performed after study drug infusion:

- Collect vital signs within 30 minutes of the end of infusion.
- Collect CBC with differential 1 hour (± 15 minutes) after the end of infusion.
- Observe the patient for at least 1 hour after the end of infusion.

Concomitant medication use and AE (including AESI and SAE) will be documented throughout the clinic visit.

12.4 Extension Day 57 (± 3) – Dose 3

The following procedures will be performed prior to study drug infusion:

- Have patient complete the SF-36 Health Survey.
- Determine body weight (in kg).
- Enter PID and weight (in kg) into IRT.
- Document any changes to baseline diet.
- Collect vital signs within 30 minutes prior to the start of infusion.
- Collect urine only if patient is of childbearing potential. Conduct a urine pregnancy test.
- Perform symptom-directed physical examination, as needed.
- Collect blood samples for CBC and chemistry.
- The study pharmacist will prepare study drug at **3 mg/kg** using the body weight obtained at the visit. The final combined volume of the IV bag of study drug + 0.9% NaCl will be **120 mL**.

Note: **100 mL** of the calculated volume of study drug/NaCl mixture will be administered to the patient. The extra 20 mL is to be used to prime the IV infusion line during the preparation of the IV line or to be left over in the infusion bag/tubing when the infusion is completed.

Procedures associated with the infusion of study drug include:

- Premedication only to be administered with the written approval of the Medical Monitor.
- Infuse 100 mL of study drug using an infusion pump over at least 2 hours, depending on the Investigator's discretion and tolerance to prior infusions. Refer to the Pharmacy Manual for infusion rates. Record the start and stop times of the infusion including any times the infusion is interrupted.
- Collect vital signs within 30 minutes after the start of infusion.
- An unscheduled ADA blood sample may be obtained if an immunogenicity-related AE is suspected. If anaphylaxis is suspected, collect a sample of blood for plasma histamine and tryptase levels within 1–2 hours of the onset of symptoms.

The following procedures will be performed after study drug infusion:

- Collect vital signs within 30 minutes of the end of infusion.
- Collect CBC with differential 1 hour (± 15 minutes) after the end of infusion.
- Observe the patient for at least 1 hour after the end of infusion.

Concomitant medication use and AE (including AESI and SAE) will be documented throughout the clinic visit.

12.5 Extension Day 85 (± 3) – Dose 4

The following procedures will be performed prior to study drug infusion:

- Have patient complete the SF-36 Health Survey.
- Determine body weight (in kg).
- Enter PID and weight (in kg) into IRT.
- Document any changes to baseline diet.
- Collect vital signs within 30 minutes prior to the start of infusion.
- Collect urine only if patient is of childbearing potential and conduct urine pregnancy test.
- Perform symptom-directed physical examination, as needed.
- Collect blood samples for CBC and chemistry.
- The study pharmacist will prepare study drug at **3 mg/kg** using the body weight obtained at the visit. The final combined volume of the IV bag of study drug + 0.9% NaCl will be **120 mL**.

Note: **100 mL** of the calculated volume of study drug/NaCl mixture will be administered to the patient. The extra 20 mL is to be used to prime the IV infusion line during the preparation of the IV line or to be left over in the infusion bag/tubing when the infusion is completed.

Procedures associated with the infusion of study drug include:

- Premedication only to be administered with the written approval of the Medical Monitor.
- Infuse 100 mL of study drug using an infusion pump over at least 2 hours, depending on the Investigator's discretion and tolerance to prior infusions. Refer to the Pharmacy Manual for infusion rates. Record the start and stop times of the infusion including any times the infusion is interrupted.

- Collect vital signs within 30 minutes after the start of infusion.
- An unscheduled ADA blood sample may be obtained if an immunogenicity-related AE is suspected. If anaphylaxis is suspected, collect a sample of blood for plasma histamine and tryptase levels within 1–2 hours of the onset of symptoms.

The following procedures will be performed after study drug infusion:

- Collect vital signs within 30 minutes of the end of infusion.
- Collect CBC with differential 1 hour (± 15 minutes) after the end of infusion.
- Observe the patient for at least 1 hour after the end of infusion.

Concomitant medication use and AE (including AESI and SAE) will be documented throughout the clinic visit.

12.6 Extension Day 113 (± 3) – Dose 5

The following procedures will be performed prior to study drug infusion:

- Have patient complete the SF-36 Health Survey.
- Determine body weight (in kg).
- Enter PID and weight (in kg) into IRT.
- Document any changes to baseline diet.
- Collect vital signs within 30 minutes prior to the start of infusion.
- Collect urine only if patient is of childbearing potential and perform urine pregnancy test.
- Perform symptom-directed physical examination, as needed.
- Collect blood samples for CBC and chemistry.
- The study pharmacist will prepare study drug at **3 mg/kg** using the body weight obtained at the visit. The final combined volume of the IV bag of study drug + 0.9% NaCl will be **120 mL**.

Note: **100 mL** of the calculated volume of study drug/NaCl mixture will be administered to the patient. The extra 20 mL is to be used to prime the IV infusion line during the preparation of the IV line or to be left over in the infusion bag/tubing when the infusion is completed.

Procedures associated with the infusion of study drug include:

- Premedication only to be administered with the written approval of the Medical Monitor.
- Infuse 100 mL of study drug using an infusion pump over at least 2 hours, depending on the Investigator's discretion and tolerance to prior infusions. Refer to the Pharmacy Manual for infusion rates. Record the start and stop times of the infusion including any times the infusion is interrupted.
- Collect vital signs within 30 minutes after the start of infusion.
- An unscheduled ADA blood sample may be obtained if an immunogenicity-related adverse event is suspected. If anaphylaxis is suspected, collect a sample of blood for plasma histamine and tryptase levels within 1–2 hours of the onset of symptoms.

The following procedures will be performed after study drug infusion:

- Collect vital signs within 30 minutes of the end of infusion.
- Collect CBC with differential 1 hour (± 15 minutes) after the end of infusion.
- Observe the patient for at least 1 hour after the end of infusion.

Concomitant medication use and AE (including AESI and SAE) will be documented throughout the clinic visit.

12.7 Extension Day 141 (± 3) – Dose 6

The following procedures will be performed prior to study drug infusion:

- Have patient complete the SF-36 Health Survey.
- Determine body weight (in kg).
- Enter PID and weight (in kg) into IRT.
- Document any changes to baseline diet.
- Collect vital signs within 30 minutes prior to the start of infusion.
- Collect urine only if patient is of childbearing potential and perform urine pregnancy test.
- Perform symptom-directed physical examination, as needed.
- Collect blood samples for CBC and chemistry.
- The study pharmacist will prepare study drug at **3 mg/kg** using the body weight obtained at the visit. The final combined volume of the IV bag of study drug + 0.9% NaCl will be **120 mL**.

Note: 100 mL of the calculated volume of study drug/NaCl mixture will be administered to the patient. The extra 20 mL is to be used to prime the IV infusion line during the preparation of the IV line or to be left over in the infusion bag/tubing when the infusion is completed.

Procedures associated with the infusion of study drug include:

- Premedication only to be administered with the written approval of the Medical Monitor.
- Infuse 100 mL of study drug using an infusion pump over at least 2 hours, depending on the Investigator's discretion and tolerance to prior infusions. Refer to the Pharmacy Manual for infusion rates. Record the start and stop times of the infusion including any times the infusion is interrupted.
- Collect vital signs within 30 minutes after the start of infusion.
- An unscheduled ADA blood sample may be obtained if an immunogenicity-related AE is suspected. If anaphylaxis is suspected, collect a sample of blood for plasma histamine and tryptase levels within 1–2 hours of the onset of symptoms.

The following procedures will be performed after study drug infusion:

- Collect vital signs within 30 minutes of the end of infusion.
- Collect CBC with differential 1 hour (± 15 minutes) after the end of infusion.
- Observe the patient for at least 1 hour after the end of infusion.

Concomitant medication use and AE (including AESI and SAE) will be documented throughout the clinic visit.

12.8 Extension Day 169 (± 3) – Dose 7

The following procedures will be performed prior to study drug infusion:

- Have patient complete the SF-36 Health Survey.
- Determine body weight (in kg).
- Enter PID and weight (in kg) into IRT.
- Document any changes to baseline diet.
- Collect vital signs within 30 minutes prior to the start of infusion.
- Collect urine only if patient is of childbearing potential and perform urine pregnancy test.

- Perform symptom-directed physical examination, as needed.
- Collect blood samples for CBC and chemistry.
- The study pharmacist will prepare study drug at **3 mg/kg** using the body weight obtained at the visit. The final combined volume of the IV bag of study drug + 0.9% NaCl will be **120 mL**.

Note: **100 mL** of the calculated volume of study drug/NaCl mixture will be administered to the patient. The extra 20 mL is to be used to prime the IV infusion line during the preparation of the IV line or to be left over in the infusion bag/tubing when the infusion is completed.

Procedures associated with the infusion of study drug include:

- Premedication only to be administered with the written approval of the Medical Monitor.
- Infuse 100 mL of study drug using an infusion pump over at least 1 hour, depending on the Investigator's discretion and tolerance to prior infusions. Refer to the Pharmacy Manual for infusion rates. Record the start and stop times of the infusion including any times the infusion is interrupted.
- Collect vital signs within 30 minutes after the start of infusion.
- An unscheduled ADA blood sample may be obtained if an immunogenicity-related AE is suspected. If anaphylaxis is suspected, collect a sample of blood for plasma histamine and tryptase levels within 1–2 hours of the onset of symptoms.

The following procedures will be performed after study drug infusion:

- Collect vital signs within 30 minutes of the end of infusion.
- Collect CBC with differential 1 hour (± 15 minutes) after the end of infusion.
- Observe the patient for at least 1 hour after the end of infusion.

Concomitant medication use and AE (including AESI and SAE) will be documented throughout the clinic visit.

12.9 Extension Day 197 (± 3) – Dose 8

The following procedures will be performed prior to study drug infusion:

- Have patient complete the SF-36 Health Survey.
- Determine body weight (in kg).

- Enter PID and weight (in kg) into IRT.
- Document any changes to baseline diet. Changes are allowed after the seventh dose has occurred and will be documented in the CRF.
- Collect vital signs within 30 minutes prior to the start of infusion.
- Collect urine only if patient is of childbearing potential and perform urine pregnancy test.
- Perform symptom-directed physical examination, as needed.
- Collect blood samples for CBC, chemistry, PK, and ADA.
- The study pharmacist will prepare study drug at **3 mg/kg** using the body weight obtained at the visit. The final combined volume of the IV bag of study drug + 0.9% NaCl will be **120 mL**.

Note: **100 mL** of the calculated volume of study drug/NaCl mixture will be administered to the patient. The extra 20 mL is to be used to prime the IV infusion line during the preparation of the IV line or to be left over in the infusion bag/tubing when the infusion is completed.

Procedures associated with the infusion of study drug include:

- Premedication only to be administered with the written approval of the Medical Monitor.
- Infuse 100 mL of study drug using an infusion pump over at least 1 hour, depending on the Investigator's discretion and tolerance to prior infusions. Refer to the Pharmacy Manual for infusion rates. Record the start and stop times of the infusion including any times the infusion is interrupted.
- Collect vital signs within 30 minutes after the start of infusion.
- An unscheduled ADA blood sample may be obtained if an immunogenicity-related AE is suspected. If anaphylaxis is suspected, collect a sample of blood for plasma histamine and tryptase levels within 1–2 hours of the onset of symptoms.

The following procedures will be performed after study drug infusion:

- Collect vital signs within 30 minutes of the end of infusion.
- Collect CBC with differential 1 hour (± 15 minutes) after the end of infusion.
- Observe the patient for at least 1 hour after the end of infusion.

Concomitant medication use and AE (including AESI and SAE) will be documented throughout the clinic visit.

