5.1 Study Overview

This is a Phase 3, multicenter, open-label, extension study to evaluate the safety and tolerability of AK002 in patients with EG and/or EoD.

Patients who complete Study AK002-016 or Study AK002-012 will have the option to receive AK002 in an open-label manner. A patient is categorized as having completed Study AK002-016 if 6 infusions of study drug are administered and the patient is followed through at least Day 176 (± 3 days). A patient is categorized as having completed Study AK002-012 if the patient received all cohort-appropriate doses and was followed for 5 months after last dose of study drug in AK002-012. During Study AK002-016X, patients will maintain the same patient number that was assigned in Study AK002-016 or Study AK002-012, as applicable.

Safety will be assessed by body weight, vital signs, symptom-directed physical examination, complete blood count (CBC) with differential, blood chemistry, urinalysis, and assessment of AE including adverse events of special interest (AESI) and serious adverse events (SAE). In addition, blood samples will be obtained for evaluation of PK and ADA.

The study is designed as follows:

- Patients completing Study AK002-016 dosing and entering the extension study may begin extended dosing 1 day after the Day 176 visit of Study AK002-016, which will be considered Extension Day 1 of Study AK002-016X.

- Patients entering the extension study but who cannot start the extension study 1 day after the Day 176 visit has occurred will remain in the main study until they receive the first dose of study drug in the extension study.
- The Day 197 and Day 225 main study visits will occur if the patient does not enroll in the extension study prior to the scheduled date of these visits. A patient enrolling in the extension study prior to Day 197 will not complete the Day 197 or Day 225 procedures under the main study.
- A patient not enrolled in the extension study on or before Day 225 in the AK002-016 study will not be able to enter the extension study.
- Patients entering the extension study within 28 (± 3) days of the last study visit in AK002-016 will not require duplicate predose labs or procedures prior to the first dosing in AK002-016X.
- Patients will receive up to 18 infusions of AK002 administered every 28 (± 3) days in an open-label manner. All infusions of AK002 will be administered at 3 mg/kg.

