9.4 Study Drug Dosage and Dose Regimen

All infusions of AK002 will be 3 mg/kg. Dosing will occur on Extension Days 1, 29, 57, 85, 113, 141, 169, 197, 225, 253, 281, 309, 337, 365, 393, 421, 449, and 477 (± 3 days).

The exact amount of AK002 to be mixed with NaCl will be calculated prior to each infusion and based on current patient body weight. Study drug will be administered as a single peripheral intravenous infusion using an infusion pump as indicated in the study Pharmacy Manual at the study visits specified in [Table 1](#).

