9.6 Study Drug Administration

Specific instructions on administration and supplies required for administration are detailed in the Pharmacy Manual. In general, study drug will be infused through a peripheral vein intravenous set. The intravenous line should be kept open before and after the infusion with sufficient quantities of 0.9% NaCl to assure patency.

A volume of 100 mL* of the calculated dose of study drug will be infused over at least 4 hours on Extension Day 1, over at least 2 hours on Extension Days 29 (± 3), 57 (± 3), 85 (± 3), 113 (± 3), and 141 (± 3) and over at least 1 hour from Extension Day 169 (± 3) and onwards. If the infusion is slowed or interrupted, the time may be extended longer than 4 hours, as long as it does not exceed 8 hours.

* Due to the rounding of the total infusion volume by some programmable infusion pumps, an infusion of 99 mL to 101 mL will be considered a complete infusion and will not be recorded as a deviation of the study.

Due to programming limitations of some infusion pumps, all volumes associated with the infusion may be rounded to the nearest 1/10th mL.

For the first infusion of study drug, patients will be premedicated with 80 mg oral prednisone (or approved equivalent) 12–24 hours prior to the start of the study drug infusion. For subsequent infusions, premedication may only be used at the discretion of the Investigator and with the written approval of the Medical Monitor.

The IV infusion may be interrupted and/or the rate may be reduced if a patient has an IRR. The time the infusion is initiated/concluded (including any interruptions) will be documented in the eCRF. If the infusion is restarted after an interruption, the infusion must be completed within 8 hours of preparation. Administration will be discontinued if, in the opinion of the Investigator,

an interrupted infusion cannot be restarted for safety reasons or if the infusion cannot be completed within 8 hours of preparation. Administration will also be discontinued in any patient experiencing a serious adverse event during the course of the infusion.

The patient will be observed at least 1 hour after the end of each infusion, as per Investigator discretion.

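### Does infusing 100 mL of a 120 mL bag mean patients receive less than the stated 3 mg/kg?

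*Combined protocol and SAP*

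**What the plan says.** Two places state the dose without qualification. Section 5.1 says "All infusions of AK002 will be administered at 3 mg/kg", and Section 9.4 says "All infusions of AK002 will be 3 mg/kg". Section 9.4 adds: "The exact amount of AK002 to be mixed with NaCl will be calculated prior to each infusion and based on current patient body weight". Table 1, note 11 (Section 5.2) has the interactive response system do that calculation from the entered body weight. Section 9.5 refers to the Pharmacy Manual for the preparation steps, and Section 11.3.2 has the dose calculation kept on a preparation worksheet.

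The volumes appear in the dosing-visit sections, 12.2 to 12.9 and 12.11. (Section 12.10 is an endoscopy visit with no infusion.) Section 12.2 reads: "The study pharmacist will prepare study drug at 3 mg/kg using the body weight obtained at the visit"; then "The final combined volume of the IV bag of study drug + 0.9% NaCl will be 120 mL"; then "100 mL of the calculated volume of study drug/NaCl mixture will be administered to the patient". The other 20 mL is accounted for by "The extra 20 mL is to be used to prime the IV infusion line during the preparation of the IV line", or is left behind in the bag or tubing.

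Section 9.6 describes the same step from the administration side. It presents the 100 mL as a volume of the calculated dose and says that "an infusion of 99 mL to 101 mL will be considered a complete infusion". It also asks for saline to keep the line open before and after the infusion, without giving a volume.

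**The concern.** The visit sections attach 3 mg/kg to the act of preparation, and the next sentence gives the bag volume as 120 mL. A reader can easily take this to mean that 3 mg/kg goes into 120 mL. Since only 100 mL is then given and the remaining 20 mL is drug mixture too, one sixth of the drug would never reach the patient. Nothing in the protocol mentions an allowance for that sixth.

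If this were so, all 18 infusions would be described at a dose higher than the one given. The stated dose anchors the description of safety, drug concentration and efficacy, and Section 3 chose 3 mg/kg by comparing dose regimens. A consistent shortfall of about 17% would therefore mislabel the exposure behind the results.

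**Working it through.** **Inputs**

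- Stated dose per infusion: 3 mg/kg (Sections 5.1 and 9.4).
- Final bag volume: 120 mL (Sections 12.2 to 12.9 and 12.11).
- Volume infused: 100 mL (same sections, and 9.6); 99 to 101 mL counts as complete (Section 9.6).
- Volume not infused by the pump: 120 − 100 = 20 mL.
- Number of infusions: 18 (Section 9.4).
- Drug content of the bag: not stated.
- Saline volume after the infusion, and tubing volume: not stated.

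**Formula.** Delivered dose = bag content (mg/kg) × volume infused / 120.

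**Can the stated dose be reproduced?** Yes, if the bag is made up so that 100 of its 120 mL carries the dose.

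- Bag content needed: 3 × 120/100 = 3.6 mg/kg.
- Delivered in 100 mL: 3.6 × 100/120 = 3.0 mg/kg, the stated figure.
- Delivered in 99 to 101 mL: 3.6 × 99/120 = 2.97 to 3.6 × 101/120 = 3.03 mg/kg, within 1% of 3 mg/kg.

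**What if the bag holds exactly 3 mg/kg in total?**

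- Delivered in 100 mL: 3 × 100/120 = 2.5 mg/kg; shortfall 1 − 100/120 = 16.7%.
- Delivered in 99 to 101 mL: 2.475 to 2.525 mg/kg, or 17.5% to 15.8% below 3 mg/kg.
- Over 18 infusions: 18 × 2.5 = 45 mg/kg against 18 × 3 = 54 mg/kg.

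**Saline through the line.** If saline carried held-up mixture into the patient, the effective volume would lie between 100 and 120 mL. With 3 mg/kg in the bag, the delivered dose would then lie between 2.5 and 3.0 mg/kg (2.75 at 110 mL). With 3.6 mg/kg in the bag, it would lie between 3.0 and 3.6 mg/kg (3.3 at 110 mL). The documents do not say how much, if any, is carried in.

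**Which reading does the text support?** The result turns on one missing number, the bag content.

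- Section 12.2 says the drug is prepared at 3 mg/kg. That can name the content of the bag or the dose level to be given.
- Section 9.6 links the infused 100 mL to the calculated dose and treats 99 to 101 mL as complete, which fits 100 mL as the dose volume.
- Section 12.2 calls the 20 mL extra and gives it a purpose, which fits an overfill.
- Sections 5.1 and 9.4 attach 3 mg/kg to the infusion, not to the bag.

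On the overfill reading, 3 mg/kg, 120 mL and 100 mL all hold together. On the bag-content reading they do not. The protocol's figures therefore do not contradict one another unless an assumption that it does not make is added.

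**The case for a change.** The strongest case for acting is that the literal reading is a natural one and the instruction is repeated in nine visit sections covering all 18 doses. Section 9.4 and Table 1, note 11 tie the amount mixed to body weight and mention no allowance for unused volume. The wording also varies: Section 9.6 speaks of 100 mL of the calculated dose, Section 12.2 of 100 mL of the calculated volume of mixture, which sounds like part of a larger total. A tolerance of 1 mL in 100 sits oddly beside an unexplained 20 mL. Section 15 describes no exposure summary that would reveal a difference, and the infusion instructions ask for times but do not mention recording the volume given.

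Part of this stands. The protocol does not say whether 3 mg/kg is what the bag holds or what the patient receives, and someone with the Pharmacy Manual and the dosing calculation could settle that quickly.

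The rest does not carry the point further. The protocol openly places the calculation and the preparation steps in other documents, so silence here is not evidence that the allowance is missing there. The stakes for the analysis are also limited. Concentrations are measured by assay (Sections 6.2 and 11.4.7), not derived from nominal dose. Section 15 plans descriptive summaries without formal inference and no exposure–response analysis. Computing delivered dose as bag milligrams × mL infused / 120 would not clearly help either: Section 15 sets out no exposure table to amend, and the formula leaves out any drug carried in by saline.

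**Conclusion.** The concern does not hold as an arithmetic error. The division is right: 100/120 of 3 mg/kg is 2.5 mg/kg, a 16.7% shortfall before any saline contribution. It applies only if the 120 mL bag holds exactly 3 mg/kg in total, which the protocol does not say. If the bag holds 3.6 mg/kg, the infused 100 mL delivers the stated 3.0 mg/kg and the shortfall is nil; the wording of Section 9.6 and the description of the 20 mL as extra are consistent with this. The documents cannot show which content is used, because the calculation sits in the interactive response system and the preparation steps in the Pharmacy Manual.

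What remains is a gap in detail that the protocol delegates to those sources. Sections 5.1, 9.4, 9.6 and the dosing visits in Section 12 should be read together with them. No dose or preparation rule is proposed here, and no change to the plan follows.
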